### Secondary objectives

- To investigate changes in adverse event-related quality of life using patient-reported questionnaires (PRO-CTCAE, Skindex 16).
- To investigate the safety/tolerability of benralizumab in patients with eosinophil-related cutaneous adverse events.
- To investigate the need for supportive medications (corticosteroids, antihistamines, immunosuppressants) in patients treated with benralizumab.
- To investigate the effect of benralizumab on subsequent planned cycles of checkpoint inhibitors (CPIs), or targeted therapies.
- To compare the effect of benralizumab on corticosteroid naïve and corticosteroid dependent/refractory ercAEs.

- To correlate the percent reduction in blood absolute eosinophil numbers and skin histology with clinical response to benralizumab.
- To investigate change in body surface area (BSA) of ercAE to quantify change in affected area in response to benralizumab over time.
- To investigate relative dose intensity (RDI) and compliance of patients' culprit anticancer therapy for the duration of the trial.

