## 4.0 OVERVIEW OF STUDY DESIGN/INTERVENTION

### 4.1 Design

This is a single-arm phase II study of patients with grade 2/3 eosinophil-related cutaneous adverse events treated with benralizumab. The primary objective is to determine the reduction of 2/3 ercAEs to grade  $\leq 1$ . Secondary endpoints are reduction in blood and skin eosinophils and its association with response, safety/tolerability of benralizumab, impact on quality of life, concomitant supportive medications, calculated rash body surface area (BSA), relative dose intensity (RDI) of anticancer therapy, and ability to continue anticancer therapy. An exploratory endpoint is analyzing blood biomarkers that correlate with benralizumab efficacy.

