## 7.2 Randomization

Not applicable

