## 13.0 CRITERIA FOR OUTCOME ASSESSMENT AND ENDPOINT EVALUABILITY

Please refer to Section 11.0 regarding the timing of ercAE assessments. Documentation (photographic) must be provided for patients removed from study for ercAE progression. Response and ercAE severity will be evaluated in this study using the Common Terminology Criteria for Adverse Events version 5.0. Changes in severity grade by specific skin/subcutaneous tissue AE term will be used.

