**Body Surface Area (BSA):** Changes in BSA of ercAE will be calculated from total body photography images taken at Week 0/Day 1, Week 4/Day 28, and Week 8/Day 56. We will use regression models and descriptive statistics to quantify change in affected BSA in response to benralizumab.

**Relative Dose Intensity (RDI):** RDI of the culprit anticancer therapy will be calculated from Week 0/ Day 1 to end of study date of the trial for each patient. Relative dosage and standard dosage will be derived based on the investigators' and primary oncologists' notes and other documentation from the electronic medical records at Memorial Sloan Kettering Cancer Center. We will use regression models to assess differences in compliance to different culprit anticancer therapies in response to benralizumab.

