## **16.2 Data Management**

A Clinical Research Coordinator (CRC) will be assigned to the study. The responsibilities of the CRC include project compliance, data collection, abstraction and entry, data reporting, regulatory monitoring, problem resolution and prioritization, and coordinating the activities of the protocol study team.

The data collected for this study will be entered into Medidata. Source documentation will be available to support the computerized patient record. Research blood collection for biomarker analysis and photographic data will be deidentified; will be labelled with patient study IDs to preserve links to clinical data. Canfield imaging systems Inc will be used to store photographic data.

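### Rash body surface area is measured from stored photographs, but nothing in the plan keeps the reader from knowing which image is before and which is after treatment

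*Combined protocol and SAP*

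**What the plan says.** BSA is a secondary objective: "To investigate change in body surface area (BSA) of ercAE to quantify change in affected area in response to benralizumab over time" (Section 2.0). Its source is given under the secondary endpoints in Section 14.1: "Changes in BSA of ercAE will be calculated from total body photography images taken at Week 0/Day 1, Week 4/Day 28", with Week 8/Day 56 as the third time point. The analysis is one sentence: "We will use regression models and descriptive statistics to quantify change in affected BSA in response to benralizumab". That paragraph names no reader, reading method, software, reading order or masking, and no hypothesis, alpha level or success threshold for BSA.

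On handling of the images, Section 16.2 says that "photographic data will be deidentified; will be labelled with patient study IDs to preserve links to clinical data". It also names the system in which photographs are stored, but does not describe how they are read.

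On design, Section 4.1 states "This is a single-arm phase II study of patients with grade 2/3 eosinophil-related cutaneous adverse events treated with benralizumab", and the entry under Section 7.2 (Randomization) is "Not applicable".

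Total body photography is scheduled for all patients at Screening, Week 0, Week 4 and Week 8 (Sections 10.0 and 11.0). Section 13.0 adds a separate documentation rule: "Documentation (photographic) must be provided for patients removed from study for ercAE progression".

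**The concern.** The CTCAE grade is assigned at visits where everyone knows the patient is on benralizumab. BSA differs because it can be read afterwards from images, so its reader need not know whether a given image is before or after treatment. The plan does not use that opportunity.

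Measuring rash area on a photograph, if done by eye, calls for judgement at borderline areas. A reader who knows that an image is from Week 4 or Week 8 may judge those areas more leniently. In a randomized trial with masked allocation such an error would fall on both arms and largely cancel. Here it goes entirely into the estimated within-patient change.

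What is at stake is the credibility of the BSA result, and its value as corroboration of the Week 4 CTCAE response. Read with knowledge of the visit, BSA can carry the same expectation bias as the grade.

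**Working it through.** **Step 1. Is there a safeguard anywhere?** The relevant provisions, side by side:

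- Section 14.1, BSA: gives image source and visits. Silent on reader, method, order and masking.
- Section 16.2: images carry a study ID in place of patient identity, and the ID is kept so that they can be linked to clinical data. This addresses privacy. It does not address visit or date.
- Section 13.0: photographic documentation for removals due to progression. Not about BSA reading or masking.
- Sections 10.0 and 11.0: when photographs are taken, not how they are read.
- Section 15.2, end-of-study reporting: the words unblinded and unblinding appear only here, in text on the SAE line listing.

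No masked assessment of any outcome is described, and no imaging manual is cited that might contain one.

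**Step 2. Why does the error not cancel?** Let B be true baseline BSA, F true follow-up BSA, and u the relative under-reading of follow-up images. The measured change is (1 − u)F − B = (F − B) − uF. The bias is −uF. With one arm there is no second term to subtract it from. If the true change is zero, F = B and the spurious fall is uB.

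**Step 3. How large could it be?** The documents give no baseline BSA, SD or effect size, so every input except n is an assumption:

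- n = 28, the number of evaluable patients named for the analyses in Section 14.1
- baseline BSA 20-30% of body surface (assumed)
- SD of change 8-15 percentage points (assumed)
- true mean change zero (assumed)
- two-sided 5% paired t-test (assumed; Section 14.1 does not specify it)

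Standardized bias d = uB/SD. The test statistic is noncentral t with 27 degrees of freedom and noncentrality d√28; the critical value is 2.052.

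| u | Baseline BSA | SD | Spurious fall | d | d√28 | False-positive rate |
|---|---|---|---|---|---|---|
| 10% | 20% | 15 | 2 points | 0.133 | 0.71 | 0.105 |
| 10% | 30% | 8 | 3 points | 0.375 | 1.98 | 0.482 |
| 20% | 20% | 15 | 4 points | 0.267 | 1.41 | 0.275 |
| 20% | 30% | 8 | 6 points | 0.750 | 3.97 | 0.969 |

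The ranges are therefore about 10-48% for 10% under-reading and 28-97% for 20%. With n = 48, the other sample size in the protocol, they become 15-72% and 44-99.9%. A larger sample makes a fixed reading bias more likely to appear significant.

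**Step 4. Which skin outcomes could be read masked?** Photographs are scheduled for every patient. Skin histology is also correlated with response (Section 2.0), and slides too could be read without knowledge of time point. But the baseline biopsy is taken only if standard care calls for it, and the Day 28 biopsy carries a condition tied to improving symptoms (Section 11.0, footnote 3), so coverage will be incomplete. Photographic BSA is thus the skin outcome most readily protected, not the only one.

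**The case against.** Five points deserve weight.

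**Silence is not a described practice.** A change score must attach each reading to a visit, which says nothing about what the reader sees. The documents do not mention manual tracing, and an automated method would leave less room for expectation. This stands: unmasked reading is permitted, not specified. It does not close the gap, because nothing rules it out.

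**The numbers are assumed.** They rest on invented inputs and on a test that Section 14.1 does not plan; the stated analysis is regression and description without an alpha level. This stands. They show only that modest under-reading could matter.

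**Masking does not make a single-arm change unbiased.** Patients enter with a grade 2/3 event that is new or worsening within 90 days and continue existing skin treatments (Section 6.1). Spontaneous improvement, regression to the mean and concomitant treatment remain. This stands. Masking removes one source of bias only.

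**Masking may be imperfect.** A reader who examined the patients may recognise them, a Day 28 biopsy site may identify a Week 8 image, and marked clearing may suggest its own time point. This stands in part: hiding the order still helps at borderline areas. A patient who qualified on pruritus without visible lesions contributes nothing to such a reading.

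**BSA decides nothing.** It is one of many secondary endpoints and has no threshold. This stands, and limits how much weight the point should carry.

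Two stronger readings are tempting and should not be drawn. A reader might infer that BSA is the only skin outcome that could be protected; histology shows otherwise. A reader might also infer from Section 13.0 that responders go undocumented because photographs are demanded only for progression; Sections 10.0 and 11.0 schedule images for every patient.

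**Conclusion.** The point holds in limited form. The plan derives a secondary endpoint from stored images in a trial where all patients are treated, and does not hide visit or image order from the reader. De-identification by study ID does not fill that gap. Any expectation bias would pass directly into the estimated BSA reduction.

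Its size cannot be estimated from the documents. The illustrative 10-48% false-positive rate for 10% under-reading depends wholly on the assumed baseline BSA, SD, zero true change and paired test, and should not be quoted as a property of this trial. The claim that masking would restore a 5% error rate is likewise true only if the true change is exactly zero.

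The primary decision rule, which rests on CTCAE response, is unaffected. This is an inexpensive improvement the sponsor should make, not a flaw that threatens the trial's main conclusion.

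**What to change.** In the BSA paragraph of Section 14.1, state that the Week 0, Week 4 and Week 8 images are given random codes with date and visit removed, are read in random order by the planned reader, and are decoded only after all readings are locked. Name the reader's role and the method of deriving BSA in the same place.

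Optionally, report the masked Week 0 to Week 4 BSA change by primary response status, in patients with visible lesions, as descriptive support for the primary result.

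Cost: a sentence or two in the plan, someone to re-code files already held, and batch rather than real-time reading. No added photograph, visit or reader is needed, and no stated sample size, alpha or power changes. It can still be applied to images already collected, provided they remain in storage. Where the planned reader also examined the patients, the report should say so, since recognition may weaken the masking.

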**Exploratory objective:**

We will measure blood biomarkers – IFN- $\gamma$ , IL-1 $\beta$ , IL-2, IL-4, IL-5, IL-6, IL-8, IL-10, IL-12p70, IL-13, TNF- $\alpha$ , tryptase – at Week 0/Day 1, Week 4/Day 28, and Week 8/Day 56. We will correlate baseline levels of each biomarker with response to benralizumab, where response will be coded as a binary value for each patient with response = 1 if a patient's ercAE reduced to grade 0 or 1, and response = 0 otherwise. We will report the difference in average value of biomarkers between the two response groups and the standard error of the difference. Next, we will correlate the response with biomarker measurements taken on Week 4/Day 28. We will also calculate the slope of each biomarker value over time for each patient and correlate the slope with the response. These are exploratory investigation, for which we will report differences in means and standard errors, but not p-values. Where relevant, we will also report these correlations separately based on the evaluable patients and those removed from the study.

## 15.0 TOXICITIES/RISKS/SIDE EFFECTS

The dose of benralizumab is 30mg SC once every 4 weeks for the first 3 doses, followed by once every 8 weeks for 3 additional doses.. Doses will be delayed for clinically significant hematologic and non-hematologic toxicities that are related to protocol therapy according to the guidelines described in sections below. Dose adjustments for hematologic toxicity are based on the blood counts obtained prior to the day of treatment.

Most common adverse reactions (incidence greater than or equal to 5%) include headache and pharyngitis. Hypersensitivity reactions (e.g., anaphylaxis, angioedema, urticaria, rash) have occurred following administration of benralizumab. These reactions generally occur within hours of administration, but in some instances have a delayed onset (i.e., days). In the event of a hypersensitivity reaction, benralizumab should be discontinued.

Systemic or topical corticosteroids should not be abruptly interrupted or discontinued upon initiation of therapy with benralizumab. Reductions in corticosteroid dose, if appropriate, should be gradual. Reduction in corticosteroid dose may be associated with systemic withdrawal symptoms and/or unmask conditions previously suppressed by systemic corticosteroid therapy. Eosinophils may be involved in the immunological response to some helminth infections. Patients with known helminth infections were excluded from participation in clinical trials. It is unknown if benralizumab will influence a patient's response against helminth infections.

Treat patients with pre-existing helminth infections before initiating therapy with benralizumab. If patients become infected while receiving treatment with benralizumab and

do not respond to anti-helminth treatment, discontinue treatment with benralizumab until infection resolves.

Across Trials 1, 2, and 3, 1,808 patients received at least 1 dose of benralizumab. The data described below reflect exposure to benralizumab in 1,663 patients, including 1,556 exposed for at least 24 weeks and 1,387 exposed for at least 48 weeks. The safety exposure for benralizumab is derived from two phase 3 placebo-controlled studies (Trials 1 and 2) from 48 weeks duration [benralizumab every 4 weeks (n = 841), every 4 weeks for 3 doses, then every 8 weeks (n = 822), and placebo (n = 847)]. While a dosing regimen of benralizumab every 4 weeks was included in clinical trials, benralizumab administered every 4 weeks for 3 doses, then every 8 weeks thereafter is the recommended dose. The population studied was 12 to 75 years of age, of which 64% were female and 79% were white.

Adverse reactions that occurred at greater than or equal to 3% incidence are shown below.

Adverse Reactions with BENRALIZUMAB with Greater than or Equal to 3% Incidence in Patients with Asthma (Trials 1 and 2)		
Adverse Reactions	BENRALIZUMAB (N= 822) %	Placebo (N=847) %
Headache	8	6
Pyrexia	3	2
Pharyngitis*	5	3
Hypersensitivity reactions†	3	3

Adverse reactions from Trial 3 with 28 weeks of treatment with benralizumab (n = 73) or placebo (n = 75) in which the incidence was more common in benralizumab than placebo include headache (8.2% compared to 5.3%, respectively) and pyrexia (2.7% compared to 1.3%, respectively). The frequencies for the remaining adverse reactions with benralizumab were similar to placebo.

In Trials 1 and 2, injection site reactions (e.g., pain, erythema, pruritus, papule) occurred at a rate of 2.2% in patients treated with benralizumab compared with 1.9% in patients treated with placebo. As with all therapeutic proteins, there is potential for immunogenicity. The detection of antibody formation is highly dependent on the sensitivity and specificity of the assay. Additionally, the observed incidence of antibody (including neutralizing antibody) positivity in an assay may be influenced by several factors including assay methodology, sample handling, timing of sample collection, concomitant medications, and underlying disease. For these reasons, comparison of the incidence of antibodies to benralizumab in the studies described below with the incidence of antibodies in other studies or to other products may be misleading.

Overall, treatment-emergent anti-drug antibody response developed in 13% of patients treated with benralizumab at the recommended dosing regimen during the 48 to 56 week treatment period. A total of 12% of patients treated with benralizumab developed neutralizing antibodies. Anti-benralizumab antibodies were associated with increased clearance of benralizumab and increased blood eosinophil levels in patients with high anti-drug antibody

titors compared to antibody negative patients. No evidence of an association of anti-drug antibodies with efficacy or safety was observed. The data reflect the percentage of patients whose test results were positive for antibodies to benralizumab in specific assays.

Long-term animal studies have not been performed to evaluate the carcinogenic potential of benralizumab. Published literature using animal models suggests that IL-5 and eosinophils are part of an early inflammatory reaction at the site of tumorigenesis and can promote tumor rejection. However, other reports indicate that eosinophil infiltration into tumors can promote tumor growth. Therefore, the malignancy risk in humans from an antibody that binds to IL-5Ra such as benralizumab is unknown.

#### Animal Data

In a prenatal and postnatal development study, pregnant cynomolgus monkeys received benralizumab from beginning on GD20 to GD22 (dependent on pregnancy determination), on GD35, once every 14 days thereafter throughout the gestation period and 1-month postpartum (maximum 14 doses) at doses that produced exposures up to approximately 310 times that achieved with the MRHD (on an AUC basis with maternal IV doses up to 30 mg/kg once every 2 weeks). Benralizumab did not elicit adverse effects on fetal or neonatal growth (including immune function) up to 6.5 months after birth. There was no evidence of treatment-related external, visceral, or skeletal malformations. Benralizumab was not teratogenic in cynomolgus monkeys. Benralizumab crossed the placenta in cynomolgus monkeys. Benralizumab concentrations were approximately equal in mothers and infants on postpartum day 7, but were lower in infants at later time points. Eosinophil counts were suppressed in infant monkeys with gradual recovery by 6 months postpartum; however, recovery of eosinophil counts was not observed for one infant monkey during this period.

#### Human Data

Of the total number of patients in clinical trials of benralizumab, 13% (n = 320) were 65 and over, while 0.4% (n=9) were 75 and over. No overall differences in safety or effectiveness were observed between these patients and younger patients, and other reported clinical experience has not identified differences in responses between the elderly and younger patients, but greater sensitivity of some older individuals cannot be ruled out.

CTCAE Version 5 will be utilized for toxicity evaluation.

### **15.1 Serious Adverse Event (SAE) Reporting**

An adverse event is considered serious if it results in ANY of the following outcomes:

- Death
- A life-threatening adverse event
- An adverse event that results in inpatient hospitalization or prolongation of existing hospitalization
- A persistent or significant incapacity or substantial disruption of the ability to conduct normal life functions
- A congenital anomaly/birth defect

- Important Medical Events (IME) that may not result in death, be life threatening, or require hospitalization may be considered serious when, based upon medical judgment, they may jeopardize the patient or participant and may require medical or surgical intervention to prevent one of the outcomes listed in this definition

Note: Hospital admission for a planned procedure/disease treatment is not considered an SAE.

SAE reporting is required as soon as the participant starts investigational treatment/intervention. SAE reporting is required for 30-days after the participant's last investigational treatment/intervention. Any event that occurs after the 30-day period that is unexpected and at least possibly related to protocol treatment must be reported.

Please note: Any SAE that occurs prior to the start of investigational treatment/intervention and is related to a screening test or procedure (i.e., a screening biopsy) must be reported.

All SAEs must be submitted in PIMS. If an SAE requires submission to the HRPP office per IRB SOP RR-408 'Reporting of Serious Adverse Events', the SAE report must be submitted within 5 calendar days of the event. All other SAEs must be submitted within 30 calendar days of the event.

The report should contain the following information:

- The date the adverse event occurred
- The adverse event
- The grade of the event
- Relationship of the adverse event to the treatment(s)
- If the AE was expected
- Detailed text that includes the following
  - An explanation of how the AE was handled
  - A description of the participant's condition
  - Indication if the participant remains on the study
- If an amendment will need to be made to the protocol and/or consent form
- If the SAE is an Unanticipated Problem

## 15.2 External AE Reporting

### Adverse Event Reporting Period

All AEs/SAEs, irrespective of attribution of causality, must be reported.

AE reporting, irrespective of seriousness, ends 30 days after the last dose of the study drug.

SAEs considered related to study drug(s) or study procedures occurring after the end of the AE reporting period (as defined above) must be reported.

If an SAE is present at the last study visit, the SAE should be followed to resolution or until the Investigator assesses the subject as stable, or the subject is lost to follow-up or withdraws consent. Resolution/stable means the subject has returned to baseline state of health or the Investigator does not expect any further improvement or worsening of the event.

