Treatment with benralizumab was also associated with reductions in blood basophils, which was consistently observed across all clinical studies. In the Phase 2 dose-ranging trial, blood basophil counts were measured by flow cytometry. Median blood basophil counts were 45, 52, 46, and 40 cells/µL in the 2 mg, 20 mg and 100 mg benralizumab and placebo groups, respectively. At 52 weeks (12 weeks after the last dose), median blood basophil counts were 42, 18, 17, and 46 cells/µL in the 2 mg, 20 mg and 100 mg benralizumab and placebo groups, respectively.

Benralizumab and placebo induced similar patterns of adverse effects. Benralizumab was characterized by a good safety profile. In fact, only mild-to-moderate and self-limiting adverse reactions occurred, such as cough, bronchitis, fever, headache, muscle spasms, dizziness, hyperhidrosis, and anxiety. After 12 weeks of treatment, anti-benralizumab antibodies were found in 6 patients, but no clinical consequence was reported. In 18 patients with severe eosinophilic and corticosteroid-dependent asthma showed that 30 mg of benralizumab,

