    - Have a negative serum pregnancy test prior to enrollment and within 14 days prior to administration of the investigational product (IP).
    - Patient must use an effective form of birth control (confirmed by the Investigator) throughout the study duration and within 16 weeks after last dose of IP.
  - Female subjects who cannot bear children as evidenced by one or more of the following:
    - Bilateral Oophorectomy
    - Bilateral Salpingectomy
    - Bilateral Salpingectomy-Oophorectomy
    - Hysterectomy
    - Menopause (no menses  $\geq$  1 year prior to treatment)
    - Surgical Sterilization (i.e., tubal ligation or blockage)

**Note:** If criteria not met, patient should be regarded as having child bearing potential

- Subject must be able to receive a subcutaneous injection.
- New/worsening ercAE within 90 days prior to study enrollment. Note: This assessment will be performed by the treating investigator.

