## 10.0 TREATMENT/INTERVENTION PLAN

- Benralizumab 30mg as a subcutaneous injection will be administered by a healthcare professional at once every 4 weeks for the first 3 doses (Week 0/Day 1, Week 4/Day 28, and Week 8/Day 56), followed by once every 8 weeks for 3 additional doses (Week 16/Day 112, Week 24/Day 168, and Week 32/Day 224), per the labeling instructions.

- Patients will also have a comprehensive physical examination at Week 0/Day 1
- Skin examination prior to benralizumab administration will be completed at Week 0/Day 1, Week 4/Day 28, Week 8/Day 56).

- Phlebotomy for CBC w differential at every visit (Screening, Week 0/Day 1, Week 2/Day 14, Week 4/Day 28, Week 8/Day 56, Week 16/Day 112, Week 24/Day 168, Week 32/Day 224, and 4 Weeks post-last dose).
- Total body photography at Screening, Week 0/Day 1, Week 4/Day 28, Week 8/Day 56,.
- Research blood collection for biomarker analysis (MSD Panel and IL-5) on Week 0/Day 1, Week 4/Day 28 and Week 8/Day 56:
  - Approximately 10 mL of blood will be collected in a green top sodium heparin Vacutainer tube. This sample will be sent to the Immune Monitoring Facility (IMF).
  - Approximately 4 mL of blood will be collected in a lavender top tube (with EDTA). This sample will be sent to Mayo Clinic.

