**Missed doses will not be made up.**

## 11.0 EVALUATION DURING TREATMENT/INTERVENTION

Study Procedures	Screening Visit (-7 days to Day 1) 	Week 0/ Day 1	Week 2/ Day 14 (+/- 3 days)	Week 4/ Day 28 (+/- 3 days)	Week 8/ Day 56 (+/- 3 days)	Week 16/ Day 112 (+/- 7 days) 	Week 24/ Day 168 (+/- 7 days) 	Week 32/ Day 224 (+/- 7 days) 	4 Weeks post-last dose (+/- 7 days)
Informed Consent	X 								
Demographics	X								
Medical history	X								
Concomitant medication review	X	X	X	X	X	X	X	X	X
Serum pregnancy test, per SOC and if applicable	X 								
Skin biopsy 	X			X					
CBC with differential	X	X	X	X	X	X	X	X	X
Comprehensive Metabolic Panel	X								
Physical exam and vital signs (HR, BP, weight, and temperature)	X								
Skin Exam (prior to Benralizumab administration)		X		X	X				
ECOG Performance Status (Appendix C)	X								
Total body photography	X	X		X	X				
Eosinophil-related Adverse Event Grading (CTCAE v5.0) (Appendix A)	X	X	X	X	X	X	X	X	X
Research blood collection for biomarker analysis (IL-5 & MSD Panel)		X		X	X				

Adverse event evaluation	X	X	X	X	X	X	X	X	X
Patient self-assessment (PRO-CTCAE (Appendix D) & Skindex 16 (Appendix B)	X	X	X	X	X	X	X	X	X
RegiSCAR Scoring System for Diagnosing DRESS Syndrome		X							
Benralizumab 30mg SC administration		X		X	X	X	X	X	

SOC, standard of care.

1. Informed consent within 45 days prior to treatment.
2. Serum pregnancy test for WOCBP within 14 days prior to treatment.
3. The baseline skin biopsy will be obtained within 30 days of treatment start, if applicable per standard of care. The biopsy at day 28 will be RNB if the patient's symptoms are improving.
4. Assessments will continue as long as the patient continues receiving benralizumab (up to 32 weeks). If a patient discontinues benralizumab, they will move to the 4 weeks post-last dose follow-up visit.
5. Screening and Week 0/Day 1 visits can be combined as long as comprehensive metabolic panel, CBC w/ differential, and pregnancy test (if applicable) are resulted to confirm eligibility prior to first benralizumab injection.

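### A patient who stops undosed at Week 16, 24 or 32 is already past the AE reporting period and the follow-up visit, because both are counted from the last dose

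*Combined protocol and SAP*

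**What the plan says.** Two clocks run from the last dose. In Section 15.2 (Adverse Event Reporting Period), "AE reporting, irrespective of seriousness, ends 30 days after the last dose of the study drug". Section 15.1 sets the same limit for serious events: "SAE reporting is required for 30-days after the participant's last investigational treatment/intervention". In Section 11.0 the only post-treatment column is 4 weeks (±7 days) after the last dose, and footnote 4 states: "If a patient discontinues benralizumab, they will move to the 4 weeks post-last dose follow-up visit".

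The dosing calendar in Section 10.0 has three doses on Days 1, 28 and 56, "followed by once every 8 weeks for 3 additional doses" on Days 112, 168 and 224. The schedule has no visit between these dates after Day 56.

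Some events stay reportable after the limit. Section 15.2 adds: "SAEs considered related to study drug(s) or study procedures occurring after the end of the AE reporting period (as defined above) must be reported". Section 15.1 adds: "Any event that occurs after the 30-day period that is unexpected and at least possibly related to protocol treatment must be reported".

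Other parts of the plan do not use the 30-day limit. The Section 11.0 table marks an AE evaluation at Weeks 16, 24 and 32. The subsection of Section 15.2 on assessing adverse events has them assessed at every evaluation time point and entered on the AE case report form.

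**The concern.** Neither clock refers to the decision to stop, and no reporting period or visit is counted from that decision. In the 8-weekly phase a decision taken at a scheduled visit comes after both clocks have run out. Footnote 4 then sends the patient to a visit whose date has passed.

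The reporting rule also makes the same event reportable or not according to what is dosed later. If a further dose is given, the 30 days start again and the whole preceding interval is covered. If the dose is withheld, perhaps because of the event, the later part of that interval drops out. The omission therefore falls only on patients who stop, who matter to the safety and tolerability objective.

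There is a smaller effect on the analysis. Section 14 uses the 4-week post-last-dose visit as a time point for quality of life and for eosinophil counts. For these patients it will be missing, or filled with data taken much later under a 4-week label.

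**Working it through.** **Inputs.** Dose days 1, 28, 56, 112, 168, 224 (Section 10.0). Visit windows ±3 days at Weeks 4 and 8, and ±7 days at Weeks 16, 24 and 32 (Section 11.0). Reporting limit 30 days after the last dose (Sections 15.1 and 15.2). Follow-up visit 28 ± 7 days after the last dose, so days 21 to 35 (Section 11.0).

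**The plan's own calendar.** Weeks 16, 24 and 32 times 7 give 112, 168 and 224, as stated. Weeks 8 to 16, 16 to 24 and 24 to 32 are each 56 days.

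**Formulas.** Days since last dose = visit day − previous dose day. Days past the reporting limit = that figure − 30. Days past the close of follow-up = that figure − 35. Ranges take both visits at the extremes of their windows.

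| Stops undosed at | Last dose | Days since dose (range) | Reporting ended | Follow-up window | Past limit (range) | Past follow-up close (range) |
|---|---|---|---|---|---|---|
| Week 16, Day 112 | Day 56 | 56 (46–66) | Day 86 | Days 77–91 | 26 (16–36) | 21 (11–31) |
| Week 24, Day 168 | Day 112 | 56 (42–70) | Day 142 | Days 133–147 | 26 (12–40) | 21 (7–35) |
| Week 32, Day 224 | Day 168 | 56 (42–70) | Day 198 | Days 189–203 | 26 (12–40) | 21 (7–35) |

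No permitted combination of windows brings the patient back inside either clock. With dose 3 given exactly on Day 56, follow-up closes on Day 91 and the Week 16 visit falls on Days 105–119, which is 14 to 28 days later.

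**Part of the interval affected.** 56 − 30 = 26 days; 26/56 = 46%.

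**Example.** An event starts on Day 95, which is 39 days after dose 3. If dose 4 is given on Day 112, reporting runs to Day 142 and the event is inside. If dose 4 is withheld, reporting ended on Day 86 and the event is outside, unless one of the exceptions applies.

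**Where the problem does not arise.**
- 4-weekly phase: the gaps are 27 and 28 days, inside both clocks. With windows the longest gap is 34 days, 4 days past the limit but still inside the 35-day follow-up window.
- Dose 6 given on Day 224: follow-up falls on Day 252 (245–259) and reporting runs to Day 254. Only a visit late in its window passes the limit, by at most 259 − 254 = 5 days.
- Stopping between visits: a patient who stops within 35 days of the last dose can still attend on time. Beyond 35 days both clocks have passed.

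**What falls outside after day 30.** Section 15.2 keeps related SAEs. Section 15.1, read broadly, keeps any unexpected and at least possibly related event. That leaves out non-serious AEs that are expected or unrelated, and SAEs that are not related. Section 15.0 names rash and urticaria among known hypersensitivity reactions, so a skin event of that kind could be classed as expected.

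**The case against.** The strongest reply is that little is lost in practice. The Week 16, 24 and 32 visits carry every assessment in the follow-up column: concomitant medication, blood count, skin-event grading, AE evaluation and questionnaires. The patient who stops there gets the full content of the follow-up visit, only later. The safety endpoint in Section 14 is built on the skin-event grade at each time point, so worsening seen at the stopping visit is graded whatever the reporting rule says. Section 14.0 gathers immune-related AEs from other clinics at the last study visit. Section 15.2 also has events that began inside the period followed to resolution or stability, and asks patients to notify pregnancies at once.

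Most of this stands. A reader might infer that the stopping event goes unrecorded, that follow-up cannot happen and that the safety profile will look cleaner than it is. The documents do not support that. They show rules that conflict: one has the event recorded at the visit, another says reporting ended weeks before. The reply does not settle which rule a site should follow, nor what footnote 4 means once its date has passed.

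A reader might also infer that 30 days is too short in itself, because basophils stayed low ("At 52 weeks (12 weeks after the last dose), median blood basophil counts were 42, 18, 17, and 46" in the 2 mg, 20 mg, 100 mg and placebo groups) and contraception is required "throughout the study duration and within 16 weeks after last dose of IP". The documents do not support this either. The low counts are a laboratory marker from asthma arms at 20 and 100 mg, not this trial's 30 mg, and the 2 mg arm was near its starting value (45 to 42). The contraception period is an eligibility condition that no section ties to AE follow-up.

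**Conclusion.** The point holds in limited form. A patient who stops undosed at Week 16, 24 or 32 has passed both the reporting limit (nominally by 26 days, at least 12) and the follow-up window (nominally by 21 days, at least 7). The same is true of a patient who stops between visits more than 35 days after the last dose. In such an interval, days 31 to 56 are reportable in full only if another dose is given, which conflicts with the instruction to assess and record AEs at the visit itself.

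The 46% is a share of calendar days, not of events or patients; the documents do not say how many patients will stop this way. The conclusion assumes that the last dose means the last one actually given and that no dose is given at the stopping visit. Patients given dose 6, or stopping at nominal timing in the 4-weekly phase, are covered. The Week 4 primary endpoint is unaffected.

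**What to change.** Reconcile Sections 15.1 and 15.2 with the schedule in Section 11.0. AE and SAE reporting should run to the later of 30 days after the last dose and the final study visit, with the visit at which stopping is decided counted as a study visit. The existing exceptions for late events stay as they are.

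Amend footnote 4 for the case where the 4-week post-last-dose date has passed. Either the stopping visit serves as the end-of-treatment assessment, or a follow-up visit is set from the decision to stop. In both cases label the data by actual time since the last dose, so that quality-of-life scores and eosinophil counts taken 42 to 70 days after a dose are not analysed as 4-week values.

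The cost is a change of wording and a few more AEs recorded; if the stopping visit serves, no procedure is added. A contact at 16 weeks after the last dose would be optional and is not part of this correction. No dose or stopping rule needs to change.
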